### **6.3 PATIENT SETS ANALYZED**

**Full analysis set (FAS):** All screened patients with informed consent, date of registration (date of creation of screening form in the eCRF), and at least one documented administration of Spiolto® Respimat® and available total CCQ score at visit 1 and visit 2.

**Treated set (TS):** All screened patients with informed consent, date of registration (date of creation of screening form in the eCRF), and at least one documented administration of Spiolto® Respimat®.

Table 6.3: 1 Patient sets analyzed

Class of endpoint	Patient set	
	TS	FAS
Primary and secondary endpoints		X
Safety endpoints	X	
Demographic/baseline	X	

## **6.5 POOLING OF CENTRES**

This section is not applicable because centre/country is not included in the statistical model.

## **6.6 HANDLING OF MISSING DATA AND OUTLIERS**

In context of CCQ, missing values will be replaced according to the corresponding manual (details are displayed in TSAP Section 7.3). No other missing data will be imputed.

## **6.7 BASELINE, TIME WINDOWS AND CALCULATED VISITS**

Baseline visit (Visit 1) will include historical and demographic data as well as registration and initial examination. Treatment with Spiolto® Respimat® will be documented at visit 2 after approximately 6 weeks of treatment. The mMRC breathlessness scale is completed by the patient at visit 1 and CCQ at visit 1 and 2. In addition, the PGE is completed by the physician at visit 1 and visit 2 as well as satisfaction survey at visit 2.

## **7. PLANNED ANALYSIS**

All analyses in this study are descriptive.

For categorical variables summary tabulations of the number and percentage within each category (with a category for missing data) of the parameter will be presented. For continuous variables number of values, mean, standard deviation, minimum, median, maximum and number of missing values will be presented. Proportion rates and 95% CI will be given when appropriate.

### **7.1 DEMOGRAPHIC AND OTHER BASELINE CHARACTERISTICS**

Only descriptive statistics are planned for this section of the report. All baseline analyses will be done for the treated set.

### **7.2 CONCOMITANT DISEASES AND MEDICATION**

Only descriptive statistics are planned for this section of the report. All analyses will be done for the treated set.

### **7.3 PRIMARY ENDPOINT**

For the primary endpoint, the percentage of patients with therapeutic success will be presented together with the 95% confidence interval, whereupon therapeutic success is defined as 0.4-point decrease in CCQ score from visit 1 to visit 2. The number and percentage of patients with and without therapeutic success will be calculated for the whole FAS set and the above mentioned subgroups.

For comparison of subgroups,  $\chi^2$ -Test or Fisher's Exact test, if  $\chi^2$ -Test is not valid, will be used and p-values will be interpreted nominally. Additionally, 95% confidence intervals for the percentage of patients with therapy success will be calculated for each subgroup analyzed.

The total CCQ score ranges from 0 to 6. A higher score is indicative of worse status. If a patient fills in two answers on one question the data will be considered as missing. Missing values will not be imputed, one answer in the subscales “symptom” and “CCQ-4” might be missing, respectively, in order to calculate the total score. The total CCQ score and the corresponding subscales are calculated as followed, in case that at least the number of required answers is available:

Scale	Items	Items required	Scoring (For details see www.ccq.nl )
Symptom	1; 2; 5; 6	3	$\frac{\text{Sum of answered questions}}{\text{Number of answered questions}}$
Functional state (CCQ-4)	7-10	3	$\frac{\text{Sum of answered questions}}{\text{Number of answered questions}}$
Mental state	3; 4	2	$\frac{\text{Item 3 + 4}}{2}$
Total CCQ score	All subscales must be calculable		$\frac{(\text{Symptom} + \text{Functional state}) * 4 + (\text{Mental state}) * 2}{10}$

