## **8.1 STUDY OBJECTIVES**

The objective of this NIS is to measure changes in clinical control by the CCQ in COPD patients receiving treatment with Spiolto® Respimat® after approximately 6 weeks in routine clinical practice.

Each of the 10 CCQ questions is scored by the patient on a 7-point scale between 0 and 6 at baseline and at the end of the observation after approximately 6 weeks. The sum of the scores divided by 10 gives the CCQ score, which measures the health and functional status. A higher CCQ score is indicative of worse status.

The functional state score is a calculation of the sum of the 4 questions (#'s 7, 8, 9, 10) divided by 4, the symptom score is calculation of the sum of the 4 questions (#'s 1, 2, 5, 6) divided by 4 and the mental state score is a calculation of the sum of the 2 questions (#'s 3, 4) divided by 2. More details will be described in the statistical analysis plan.

A change of 0.4 points is considered to be the MCID for the total CCQ score [XLIV].

**Primary objective:** Assess the proportion of patients achieving “therapeutic success” (0.4 point decrease in the CCQ score between baseline and after approximately 6 weeks of treatment).

**Secondary objectives** are assessment of changes in CCQ and in the CCQ symptom, mental state and functional state domains from visit 1 (baseline visit at the start of the study) to visit 2 (final visit at the end of the study, approx. 6 weeks after visit 1), the patient's general condition (physician's evaluation) at visit 1 and at visit 2, as well as patient satisfaction with Spiolto® Respimat® and willingness to continue treatment with Spiolto® Respimat® at visit 2 as proxy for adherence.

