### **9.3.2 Outcomes**

#### **9.3.2.1 Primary outcome**

“Therapeutic success” approximately 6 weeks at visit 2 (0.4 point decrease in the Clinical COPD Questionnaire - CCQ score from visit 1 to visit 2).

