## **9.5 STUDY SIZE**

We assume that patients treated with Spiolto® Respimat® will have a CCQ therapeutic success rate similar to the SGRQ responder rate considering the following:

- 1) CCQ has the great advantage of simplicity for the patient, having a very good correlation (rho = 0.67 to rho = 0.72) with the St George respiratory questionnaire (SGRQ) [XLV].
- 2) In TONADO studies [XXI] patients treated with Spiolto® Respimat® had a 57.5% SGRQ responder rates after 24 weeks.

The TONADO had a selected trial population, so a real world population would probably show somewhat lower numbers due to the wide diversity of potential patients that will be followed up. Therefore a 50% CCQ responder rate is a reasonable assumption.

Assuming a 50% therapeutic success rate for CCQ and a sample size of 4050 patients, the 95% confidence interval for the therapeutic success rate would be between 48.5% (lower limit) and 51.5% (upper limit).

To account for a 10% drop-out rate, the sample size becomes approximately 4500patients.

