### **3. INTRODUCTION**

As per ICH E9, the purpose of this document is to provide a more technical and detailed elaboration of the principal features of the analysis described in the protocol, and to include detailed procedures for executing the statistical analysis of the primary and secondary variables and other data.

This TSAP assumes familiarity with the Clinical Trial Protocol (CTP), including Protocol Amendments. In particular, the TSAP is based on the planned analysis specification as written in CTP Section 9.7 "Data Analysis". Therefore, TSAP readers may consult the CTP for more background information on the study, e.g., on study objectives, study design and population, treatments, definition of measurements and variables, planning of sample size, randomization.

SAS® Version 9.4 or higher will be used for all analyses.

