## **5. ENDPOINT(S)**

### **5.1 PRIMARY ENDPOINT(S)**

The primary endpoint of the presented study is “therapeutic success” at visit 2 i.e. approximately 6 weeks after starting treatment, defined as 0.4-point decrease in the total CCQ score between visit 1 and visit 2.

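### Does stating success as a 0.4-point CCQ decrease, with no inequality or rounding rule, put the primary success rate at risk?

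*SAP*

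**What the plan says.** The primary endpoint appears in several places in nearly the same words. SAP 5.1 has it "defined as 0.4-point decrease in the total CCQ score between visit 1 and visit 2", SAP 7.3 repeats that "therapeutic success is defined as 0.4-point decrease in CCQ score from visit 1 to visit 2", and Protocol 9.3.2.1 gives "0.4 point decrease in the Clinical COPD Questionnaire - CCQ score from visit 1 to visit 2". The objectives table at the front of the protocol puts an equals sign before the figure, which reads most naturally as *namely*. Nowhere is there a greater-than-or-equal sign or a rule on decimals. The sign was probably not lost in text extraction, because it survives in the age criterion of both documents.

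The basis for the figure is in Protocol 8.1: "A change of 0.4 points is considered to be the MCID for the total CCQ score". Protocol 9.5 treats the endpoint as a responder rate: "Therefore a 50% CCQ responder rate is a reasonable assumption". Protocol 8.1 defines the total as the sum of ten items, each scored 0 to 6, divided by 10. SAP 7.3 gives an equivalent formula from the subscales and allows one missing item in each of the symptom and functional subscales. On software, SAP 3 says "SAS® Version 9.4 or higher will be used for all analyses".

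**The concern.** The cut-off falls on a value that the change score can take. With complete questionnaires the total lies on a 0.1 grid, so some patients will fall by exactly 0.4, and the rule must say how they count. The text leaves two openings.

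The first is the wording. Read literally, it could mean exactly 0.4, more than 0.4, or at least 0.4.

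The second is numerical. Tenths have no exact binary representation, so subtracting two stored scores can give a value just below 0.4. An at-least-0.4 test then fails a patient who met the threshold. For complete scores tested as at least 0.4, the error goes one way only: no pair less than 0.4 apart passes.

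The same flag feeds the only primary endpoint and every subgroup percentage. A loss larger than the planned precision would bias the study's main reported figure.

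**Working it through.** **1. The plan's own precision.** Protocol 9.5 uses p = 0.50 and n = 4050. The half-width is 1.96 × √(0.5 × 0.5 / 4050) = 0.0154, so the interval is 48.46% to 51.54%. This agrees with the stated 48.5% to 51.5%. Allowing for 10% drop-out, 4050 / 0.9 = 4500, also as stated.

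**2. Which reading of the wording works.** With visit 1 SD 0.8 to 1.2, mean change −0.4 and SD of change 0.5 to 1.2 (all assumptions), about 3.3% to 8.2% of patients change by exactly −0.4. A success rate defined as exactly 0.4 could not come near the assumed 50%, so the sample-size section excludes that reading. A strict more-than-0.4 rule would reject patients who reach the minimal important difference itself, contrary to Protocol 8.1. A fall of 0.4 or more remains.

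**3. The rule in ordinary arithmetic.** Complete totals are k/10 with k = 0 to 60. Pairs exactly 0.4 apart are (k, k − 4) for k = 4 to 60, which gives 57 pairs. All 57 are successes. An item-sum fall of at least 4 is the same rule.

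**4. The rule in double precision.** This was computed in Python; SAS was not run. Over all 25 × 25 × 13 complete subscale combinations, the SAP 7.3 formula returns the same stored value as k/10. The 57 pairs then give:

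| Coding of a fall of at least 0.4 (V1, V2 = totals at visits 1 and 2) | Exact-0.4 pairs failed |
|---|---|
| V1 − V2 ≥ 0.4, unrounded | 31 of 57 |
| V2 − V1 ≤ −0.4, unrounded | 31 of 57 |
| V2 ≤ V1 − 0.4 | 13 of 57 |
| V1 ≥ V2 + 0.4 | 10 of 57 |
| Difference rounded before the test | 0 of 57 |
| Item sums compared | 0 of 57 |

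These are shares of possible score pairs, not of patients.

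**5. From pairs to patients.** The documents give no CCQ mean, SD or SD of change. The assumed grid had visit 1 mean 1.2 to 3.0, SD 0.8 to 1.2, mean change −0.4 and SD of change 0.5 to 1.2, giving 72 settings of 400,000 simulated patients each. The fall in the success rate was:

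- direct unrounded subtraction: 1.3 to 5.8 points, above 1.5 in 69 of 72 settings (0.013 × 4050 ≈ 53 to 0.058 × 4050 ≈ 235 patients);
- V2 ≤ V1 − 0.4: 0.2 to 2.0 points, above 1.5 in 5 of 72;
- V1 ≥ V2 + 0.4: 0.2 to 1.1 points, above 1.5 in none;
- rounded difference: zero.

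**6. Missing items.** With a permitted missing item, totals lie on multiples of 1/30. The nearest true failure is a fall of 11/30 = 0.367. Rounding the difference to four decimals leaves it a failure. Rounding to one decimal would turn it into 0.4.

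**The case for a change.** The case for a change is that a SAP exists to supply technical detail, and here the detail decides the primary endpoint. Direct subtraction is the obvious way to code a change score. Rounding the two scores first, a natural precaution, still fails 31 of 57 pairs. One sentence would close the gap. On most of the assumed distributions the loss under that coding exceeds the precision for which the study was sized.

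The arithmetic behind this stands, and so does the observation that the inequality is unwritten. What does not stand is the step from there to a defect in the plan. The SAP defines a score and a threshold in decimal numbers, and under that definition an exact 0.4 fall is a success. A program that says otherwise is wrong against the SAP. How to compare stored decimals belongs in programming specifications and checks. Neither document shows any code, so the larger losses need both a particular unseen coding and an assumed distribution. SAP 7.3 also refers to an external source for scoring details. Whether that source sets a precision rule cannot be checked here.

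**Conclusion.** The concern does not call for a change. The missing inequality is a gap that analysts fill in only one sensible way, because the minimal important difference and the responder-rate assumption both point to a fall of 0.4 or more. The rounding question concerns implementation: the plan followed as written gives the right classification for every patient.

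The possible effect runs from zero to 5.8 points on the success rate. The upper end rests on unrounded subtraction, complete questionnaires and CCQ distributions that are assumptions throughout. The consequence would also be bounded. SAP 7 makes all analyses descriptive, Protocol 9.7 plans no formal hypothesis testing, and the subgroup p-values in SAP 7.3 are nominal. The mean CCQ change in SAP 7.4 does not use the cut-off at all.

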## **9.7 DATA ANALYSIS**

### Planned analyses

More details will be described in the statistical analysis plan (SAP).

No formal hypothesis testing will be performed since this is a self-controlled study.

All patients who have received at least one dose of Spiolto® Respimat® will be included in the analysis; this is the treated set. All analyses will be performed on the treated set (as-treated analysis). If patients have missing values for an outcome, those patients will be excluded for that outcome's analysis. For example, if a patient is missing the CCQ score at

Visit 1 and/ or Visit 2, that patient will be excluded from the analyses for the primary endpoint of therapeutic success and the secondary endpoint of change in CCQs from Visit 1 to Visit 2.

The assessment will be carried out using SAS® software. The statistical characteristics presented in the end-of-text tables will be N / mean / SD / min / median / max for continuous variables. Tabulations of relative and absolute frequencies will be presented for categorical variables. Proportion rates and 95% CI will be given when appropriate.

The analyses will relate to the following data:

- Patient demographics (gender, age, height, weight)
- Comorbidities (main diagnosis and concurrent diagnosis according to MedDRA, version valid as at the time of database closure)
- COPD related and other concomitant medication (according to the WHO classification, version valid at the time of database closure)
- History of smoking
- Reported exacerbations
- Breathlessness based on mMRC score at visit 1
- Therapeutic success based on CCQ score; primary outcome
- Changes from Visit1 to Visit 2 in the CCQ and CCQ symptom, mental state and functional state scores; secondary outcome
- Patient reported daily average number of puffs of COPD rescue medication (eg. SABA, like Salbutamol) at the week before Visit 1 and the week before Visit 2
- Patient satisfaction with Spiolto® Respimat® at visit 2 only; secondary outcome
- General condition of the patient: evaluated by the physician (Physician's Global Evaluation (PGE)), secondary outcome
- Willingness to continue; secondary outcome
- Adverse Drug Reactions (ADR & SADR), fatal AEs, pregnancies
- GOLD spirometric classifications (1, 2, 3, 4) and GOLD patient groups (B, C, D)
- Details of treatment with inhaled respiratory agents before the study
- Details of treatment with respiratory agents during the study
- Reasons for ending treatment during the observation period

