### **5.4 OTHER VARIABLE(S)**

Other variables will be baseline characteristics and patient’s characteristics such as age, gender, height and weight. Additionally information about concomitant medication, diseases, therapy data, further therapies and comorbidities will be collected as well as about smoking status, exacerbation history, mMRC and GOLD group.

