#### **7.4 SECONDARY ENDPOINT(S)**

All analysis will be descriptive and will be performed on FAS. For general condition of patients and patient's satisfaction with Spiolto® Respimat® as well as the willingness to continue the treatment, the number and percentage of patients within each category will be displayed. For absolute changes in CCQ scores (symptom, functional state (CCQ-4), mental state and total scale) summary statistics will be provided.

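### Do the nominal subgroup p-values in SAP 7.3 require visit 1 CCQ to be shown by subgroup?

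*SAP*

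**What the plan says.** The primary endpoint in SAP 5.1 is "defined as 0.4-point decrease in the total CCQ score between visit 1 and visit 2". SAP 7.3 adds that "The total CCQ score ranges from 0 to 6", with higher values worse. It then plans the number and percentage of successes in the FAS and in each subgroup, a 95% confidence interval per subgroup, and a chi-square or Fisher's exact test between subgroups, which "will be used and p-values will be interpreted nominally". No covariate or stratification is mentioned.

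On visit 1 level, the visible sections say this:

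- SAP 7.4: "For absolute changes in CCQ scores (symptom, functional state (CCQ-4), mental state and total scale) summary statistics will be provided". Visit 1 levels are not named.
- SAP 5.4 lists other variables, including "smoking status, exacerbation history, mMRC and GOLD group", but not CCQ.
- SAP 7.1: "All baseline analyses will be done for the treated set". The subgroup success rates use the FAS.
- SAP 4 extends subgroup analyses to all secondary endpoints. These include the CCQ changes and PGE, and SAP 5.2 defines PGE at visit 1 as well as visit 2.

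On the status of the tests, protocol 9.7 says "No formal hypothesis testing will be performed since this is a self-controlled study", and SAP 7 says "All analyses in this study are descriptive".

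**The concern.** A patient with visit 1 CCQ below 0.4 cannot fall by 0.4. A subgroup with more such patients will show fewer successes even if the treatment does the same for everyone who has room to improve. If the report then shows a crude difference with a small p-value and no visit 1 CCQ beside it, a reader may conclude that one type of patient responds better. The word nominal warns about multiplicity and the lack of a formal claim; it does not warn about baseline level. With about 4050 patients, modest differences will reach p < 0.05. The p-values also sit uneasily with a protocol that rules out formal testing and a SAP that calls everything descriptive. Only subgroup statements are at stake; the overall success percentage is not.

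**Working it through.** **1. The plan's own figures (protocol 9.5).** Inputs: 50% success, 4050 patients, 10% drop-out.

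- Half-width = 1.96 × √(0.5 × 0.5 / 4050) = 1.54 points, so the interval is 48.46% to 51.54%. The stated 48.5% to 51.5% is reproduced.
- 4050 / 0.9 = 4500. Reproduced.

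**2. Smallest observed subgroup difference with p < 0.05.** Formula: 1.96 × 0.5 × √(1/n1 + 1/n2), total 4050. The splits are assumptions.

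| Split | n1, n2 | Difference |
|---|---|---|
| 50/50 | 2025, 2025 | 3.1 points |
| 30/70 | 1215, 2835 | 3.4 points |
| 10/90 | 405, 3645 | 5.1 points |

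**3. Size of the floor effect alone.** The documents give no CCQ mean or SD, so every input here is assumed: visit 1 SD 1.0, the same underlying improvement in both subgroups (mean 0.45, SD 0.65, independent of visit 1), scores clipped to 0–6 and rounded to 0.1. After rounding, below 0.4 means below 0.35 on the continuous scale; for mean 1.4 this is Φ(0.35 − 1.4) = Φ(−1.05) = 14.7%.

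| Visit 1 means | Below 0.4 | Success | Gap |
|---|---|---|---|
| 1.4 vs 1.8 | 14.7% vs 7.3% | 47.9% vs 52.1% | 4.2 points |
| 2.2 vs 2.6 | 3.2% vs 1.2% | 54.2% vs 55.5% | 1.3 points |

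The second gap is below every threshold in step 2; the chance of p < 0.05 is about 8% (10/90) to 13% (50/50). With a gamma distribution of the same mean and SD, the gaps are about 4.3 and 0.1 points. The floor matters only if visit 1 scores are low and the subgroups also differ clearly at visit 1. Here the assumed difference is 0.4, as large as the MCID in protocol 8.1.

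**4. Would a visit 1-adjusted model be safer?** Simulation: 400 replicates, n 4050, subgroup share 30%, visit 1 SD 1.0, subgroup differences at visit 1 of 0.2 or 0.4, slopes of change on visit 1 of −0.15 or −0.30. Percentage of runs with p < 0.05:

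| Visit 1 mean | Truth assumed | Crude test | Adjusted logistic |
|---|---|---|---|
| 2.2 | equal response at a given observed visit 1 score | 24–98% | 3–6% |
| 2.2 | equal true improvement, slope due to measurement error | 4–7% | 17–96% |
| 1.4 | equal response at a given observed visit 1 score | 57–100% | 5–6% |
| 1.4 | equal true improvement, slope due to measurement error | 12–50% | 11–96% |

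The Monte Carlo standard error at 5% is √(0.05 × 0.95 / 400) = 1.1 points, so 4–7% is compatible with the nominal 5%. Which analysis misleads depends on why change is related to visit 1 score, and the documents do not settle that.

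**5. What the visible text can prove.** The SAP contents list runs from 5.2 to 5.4, 6.3 to 6.5 and 7.4 to 7.6. The history table shows that 6.4 held the subgroup material. The text supplied therefore cannot establish that visit 1 CCQ by subgroup is absent from the plan. SAP 5.4 and 7.1 do not exclude it either: 5.4 covers variables other than the endpoints, and 7.1 lists no variables. By SAP 6.3, the treated set and the FAS differ only in whether total CCQ is available at both visits.

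**The case for a change.** The best case for a change is that the remedy is cheap and the risk is built into the endpoint. Every FAS patient has a visit 1 total CCQ by definition, so one table by subgroup, with the percentage below 0.4, needs no new data. CCQ change by subgroup shows how far patients moved, not where they started. PGE at visit 1 is a physician's rating and does not show who could reach a 0.4-point fall. The nominal label answers a different question, and under the low-baseline assumption a 4.2-point gap exceeds the 3.1- and 3.4-point thresholds without any difference in underlying improvement.

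The floor logic stands, and so does the observation that no visible section plans the table. It would be good reporting. What does not stand is that the plan is wrong without it. Visit 1 means and the share below 0.4 would show whether a floor is plausible, but would not separate a floor effect, regression to the mean and a real difference in response. Removing the p-values or relabelling them exploratory changes little when they are already nominal within an analysis declared descriptive. A nominal p-value drives no decision here, so the tension with protocol 9.7 is one of wording.

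**Conclusion.** No change to the plan is needed. No rule in SAP 7.3 yields a wrong result: the overall success rate is unaffected, and the crude subgroup percentages with their 95% intervals correctly describe how many patients met the endpoint. The floor is real, but its size cannot be derived from the documents. It is 1.3 to 4.2 points under the clipped-normal assumptions above, against 3.1 to 5.1 points needed for nominal significance at n 4050 and 50% success. At a visit 1 mean of 2.2 with equal true improvement, the crude test rejects at about its nominal rate (4–7%); at a mean of 1.4 it rejects more often (12–50%). An adjusted model exchanges one risk for another.

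Analysts can set visit 1 total CCQ beside the subgroup rates within the descriptive framework of SAP 7, if a section not supplied does not already provide it. That is helpful context for the report, not a correction. This conclusion rests on the subgroup comparisons being read as the SAP labels them: nominal and descriptive.
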